7.4. Deviation from Analyses Planned in Protocol

7.4.1. Additional analyses

The following analyses are added even though they are not included in the protocol:

- Interim analysis.
- Subgroup analyses on the secondary endpoint by patient's primary efficacy endpoint (responder vs. non-responder).

The following analyses have been added as a result of the impact of Covid-19 on the study which may result in a larger anticipated number of subjects not completing the study and therefore not undergoing the assessments required for the primary efficacy endpoint or the study being stopped prematurely by sponsor decision. This is in line with FDA Guidance on Conduct of Clinical Trials of Medical Products during COVID-19 Pandemic Guidance for Industry, Investigators, and Institutional Review Boards.

- Additional analyses suggested to primary endpoint as sensitivity analyses to determine if the impact that these have on the conclusions of the study and to describe the impact of Covid-19 on the study performance.
- A sensitivity analysis which limited the analysis to results processed in the central laboratory to determine if this resulted in different conclusions to those found from the full analysis to determine consistency in laboratory testing between central and local laboratories.
- Kaplan-Meier analysis of withdrawal from study by treatment arm and presence of tophus to determine if subjects withdraw from the study in different proportions and at different rates within the treatment groups and depending on the presence of tophus.
- Kaplan-Meier analysis of withdrawal from study due to an adverse event by treatment arm and presence of tophus to determine if subjects experience adverse events in different proportions and at different rates within the treatment groups and depending on the presence of tophus.
- Poisson regression with number of gout flares experienced during treatment periods 1-6 as the dependent variable, treatment and the presence of tophus as independent variables and length of follow up as a covariate. The ITT population would be used to conduct this analysis. Similar analysis is done for periods 4-6.

This document is confidential.

8. Safety

The population used for safety analyses will be the Safety Set (SS). Safety will be assessed on the basis of adverse event (AE), clinical laboratory data, ECG parameters, physical examinations, and vital signs.

8.1. Extent of Exposure

Frequency counts of number of patients who received all doses (i.e., completed study treatment) and descriptive statistics of doses and total cumulative doses by treatment group (SEL-212 or KRYSTEXXA®) will be presented.

Number and percentage of patients who met stopping rules will be summarized by treatment group and treatment period. The percentage will be plotted versus treatment period by treatment. The comparison between the treatment groups will be tested using CMH-test stratified by tophus presence (Yes/No).

8.2. Treatment Compliance

Treatment compliance is defined as patients receiving study drug as planned.

Compliance = $100\% \times (\text{total volume infused}) \backslash (\text{total volume planned})$

For patient who has received SEL-202, compliance will be calculated for SEL-110.36 and SEL-037.

For patient who has received KRYSTEXXA®, compliance will be calculated for KRYSTEXXA®.

Total duration of infusion as well as total time duration between start of infusion and stop of infusion will be descriptively summarized by study drug and dosing time point.

The date and time of the start and stop of drug administration, total infusion duration and volume infused will be listed.

8.3. Adverse Events / Adverse Drug Reactions

All AEs will be coded and grouped into Preferred Terms (PT) by System Organ Class (SOC), using the most recent MedDRA Version. All AEs will be summarized by treatment, SOC and PT. A treatment-emergent AE (TEAE) is an AE that starts or worsens at any time after initiation of study drug on Day 0 of Treatment Period 1 until the End of Study Visit (30 days after completion of the last dose of study drug).

An overall summary will be provided of the number and percentage of patients reporting TEAEs, serious TEAEs, treatment-related (possibly related and related) TEAEs, Adverse events of special interest (AESIs), TEAEs leading to study drug withdrawal, and TEAEs leading to death. AESIs will be defined by medical monitor prior to database lock.

The number and percentage of patients with TEAEs / serious TEAEs / TEAEs leading to study drug withdrawal/treatment-related TEAEs will be summarized by SOC and PT for each treatment group (SEL-212 or KRYSTEXXA®). AESIs will also be summarized.

TEAEs will also be summarized by maximum intensity and causality.

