7. INVESTIGATIONAL PLAN

7.1 Overall Study Design

This study is a randomized, open-label, parallel-arm study to compare the safety and efficacy profiles of SEL-212 and KRYSTEXXA. Approximately 150 patients will be randomized 1:1 prior to Baseline to receive treatment with SEL-212 or KRYSTEXXA for 6 months. Efficacy assessments, as measured by SUA levels, will be conducted at intervals that are appropriate to determine treatment effect differences, including at month 3 and month 6. Assessments of qualitative endpoints will be conducted on an assessor-blinded basis. Safety will be monitored throughout the study.

The study will be divided into 3 study periods: Screening, Treatment, and Follow-up, described below. The study is depicted schematically in [Figure 1](#).

The total duration of participation in the study will range from approximately 26 to 31 weeks (184 to 219 days) for patients randomized to SEL-212 and approximately 28 to 33 weeks (198 to 233 days) for patients randomized to KRYSTEXXA as follows:

- Screening and/or washout and premedication period: up to 45 days (up to 6.5 weeks)
- Treatment: 168 days (24 weeks) for SEL-212 KRYSTEXXA
- Safety Follow-Up: 30 (+ 4) days after the date of last infusion
 - SEL-212: Last scheduled infusion on Study Day 140
 - KRYSTEXXA: Last scheduled infusion on Study Day 154

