12.2.3 Reporting Adverse Events

12.2.3.1 Adverse Event Reporting Period

The study period during which AEs must be reported is from the time the patient is dosed until the 30 days after the last infusion of study drug. During the Screening Phase (from time informed consent is signed up to the time of dosing) any clinically significant changes in the patient's health will be recorded in the patient's medical history and will not be considered as AEs.

Investigators are not obligated to actively seek AEs or SAEs in former study patients. However, if the Investigator learns of any SAE, including a death, at any time after a patient has been discharged from the study, and he/she considers the event reasonably related to the study drug, the Investigator should promptly notify the Sponsor.

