13.5 Safety Analyses

13.5.1 Extent of exposure:

Frequency counts of number of patients who received all doses (i.e., completed study treatment) and descriptive statistics of doses and total cumulative doses by treatment group (SEL-212 or KRYSTEXXA) will be presented.

13.5.2 Adverse Events / Adverse Drug Reactions:

All AEs will be coded and grouped into Preferred Terms (PT) by System Organ Class (SOC), using the most recent MedDRA Version. All AEs will be summarized by SOC and PT.

An overall summary will be provided of the number and percentage of patients reporting TEAEs, serious TEAEs, treatment-related TEAEs, AESIs, TEAEs leading to withdrawal, and TEAEs leading to death.

The number and percentage of patients with TEAEs / serious TEAEs / TEAEs leading to withdrawal/treatment-related TEAEs will be summarized by SOC and PT for each treatment group (SEL-212 or KRYSTEXXA). AESIs will also be summarized.

TEAEs will also be summarized by maximum intensity and causality.

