3.3. Overall Study Design

This study is a randomized, open-label, parallel-arm study to compare the safety and efficacy profiles of SEL-212 and KRYSTEXXA®. Approximately 150 patients will be randomized 1:1 prior to Baseline to receive treatment with SEL-212 or KRYSTEXXA® for 6 months. Efficacy assessments, as measured by SUA levels, will be conducted at intervals that are appropriate to determine treatment effect differences, including at month 3 and month 6. Assessments of qualitative endpoints will be conducted on an assessor-blinded basis. Safety will be monitored throughout the study.

The study will be divided into 3 study periods: Screening, Treatment, and Follow-up, described below. The study is depicted schematically in the figure below:

The total duration of participation in the study will range from approximately 26 to 31 weeks (184 to 219 days) for patients randomized to SEL-212 and approximately 28 to 33 weeks (198 to 233 days) for patients randomized to KRYSTEXXA® as follows:

- Screening and/or washout and premedication period: up to 45 days (up to 6.5 weeks)
- Treatment: 168 days (24 weeks) for SEL-212 KRYSTEXXA®

- Safety Follow-Up: 30 (+ 4) days after the date of last infusion
 - SEL-212: Last scheduled infusion on Study Day 140
 - KRYSTEXXA®: Last scheduled infusion on Study Day 154

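### SAP 8.3 compares adverse events between arms as crude patient percentages, although the TEAE window differs by arm (170 versus 184 days on a full course, shorter after early stopping); time at risk should be reported beside them

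*SAP*

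**What the plan says.** **Window.** SAP 8.3 counts a TEAE from the first dose "until the End of Study Visit (30 days after completion of the last dose of study drug". Protocol 12.2.1.1 has the same definition. Protocol 12.2.3.1 sets the reporting period "from the time the patient is dosed until the 30 days after the last infusion of study drug".

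**Schedule.** Protocol 7.1 gives "SEL-212: Last scheduled infusion on Study Day 140" and "KRYSTEXXA: Last scheduled infusion on Study Day 154". SAP 3.3 repeats both, with "Safety Follow-Up: 30 (+ 4) days after the date of last infusion".

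**Stopping.** Under Protocol 7.4.1.1, a SEL-212 patient is withdrawn from drug on one Day 21 serum uric acid (SUA) value: above 1.0 mg/dL in Treatment Period 1, or above 6.0 mg/dL in Periods 2 to 5. Under Protocol 7.4.1.2, a Krystexxa patient is withdrawn on two consecutive pre-dose values above 6.0 mg/dL. In both arms withdrawn patients keep attending to the end of Period 6.

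**Summaries.** SAP 8.3: "An overall summary will be provided of the number and percentage of patients reporting TEAEs, serious TEAEs", then related TEAEs, AESIs, TEAEs leading to drug withdrawal and TEAEs leading to death. Protocol 13.5.2 is the same in substance. Neither section plans a rate per time at risk or a cumulative incidence. SAP 8.1 summarises doses and stopping-rule withdrawals, but not time at risk.

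**Use.** Safety and tolerability against Krystexxa is a stated endpoint (Protocol 6.2.3, SAP 4.3).

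**The concern.** A crude percentage depends on how often events occur and on how long patients are watched for them. Here the watching time is set by the last dose, and the last dose depends on arm: by the dosing schedule for those who finish, and by different SUA rules for those who stop. Two drugs with the same event rate would then show different percentages. What is at stake is the comparative safety statement. A gap of a few points could reflect observation time, or observation time could hide a real gap, and the planned TEAE tables carry no denominator in time from which to tell.

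**Working it through.** **1. Check the day counts against the plan's own figure.** Maximum participation = screening + last infusion day + follow-up. SEL-212: 45 + 140 + 34 = 219 days. Krystexxa: 45 + 154 + 34 = 233 days. Both match the printed maxima, so the components can be relied on.

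**2. TEAE window, full course.** Last dose + 30: SEL-212 140 + 30 = 170 days; Krystexxa 154 + 30 = 184 days. The difference is 14 days, and 14/184 = 7.6%.

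**3. TEAE window, earliest rule-based stop.** SEL-212: high value at Period 1 Day 21, last dose Day 0, window 30 days. Krystexxa: high pre-dose values at Days 14 and 28, last dose Day 14, window 14 + 30 = 44 days. If the Day 28 dose is given before that day's result is known (the earlier sample is optional), the window is 28 + 30 = 58 days.

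**4. Schedule difference alone.** Assume the same constant hazard in both arms and all doses given. With P the Krystexxa percentage over 184 days, the SEL-212 percentage is 1 - (1 - P)^(170/184).

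| Krystexxa | SEL-212 | Gap (points) |
|---|---|---|
| 10% | 9.3% | 0.7 |
| 20% | 18.6% | 1.4 |
| 50% | 47.3% | 2.7 |
| 70% | 67.1% | 2.9 |

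The largest possible gap is 2.9 points. In the 50% row the rate is ln 2 / 184 × 365.25 = 1.38 per patient-year in both arms, so a rate per time at risk would show no difference.

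**5. Adding early stopping.** The documents give no stopping pattern, so this is assumed. Stopped patients lose SUA control at a time spread evenly over Days 0–28, 0–84 or 0–140, identically in both arms, and each arm's rule is applied visit by visit. The Krystexxa window is then 0 to 28 days longer than the SEL-212 window, 14 on average. The share not stopped is 65% in both arms, 44% in both arms, or 65% (SEL-212) and 44% (Krystexxa), borrowing the responder rates in SAP 3.5 as a proxy. Gaps are Krystexxa minus SEL-212, in points, for a hazard giving 20 / 50 / 80% over 184 days.

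| Not stopped (SEL-212 / Krystexxa) | Loss over days | Mean window (days) | Gap at 20 / 50 / 80% |
|---|---|---|---|
| 65% / 65% | 0–28 | 123 vs 137 | +1.5 / +3.3 / +4.7 |
| 65% / 65% | 0–84 | 133 vs 147 | +1.4 / +3.2 / +4.1 |
| 65% / 65% | 0–140 | 143 vs 157 | +1.4 / +3.1 / +3.7 |
| 44% / 44% | 0–28 | 96 vs 110 | +1.5 / +3.7 / +6.0 |
| 44% / 44% | 0–84 | 111 vs 125 | +1.5 / +3.5 / +5.0 |
| 44% / 44% | 0–140 | 127 vs 141 | +1.4 / +3.3 / +4.3 |
| 65% / 44% | 0–28 | 123 vs 110 | -1.5 / -3.5 / -4.6 |
| 65% / 44% | 0–84 | 133 vs 125 | -0.9 / -2.0 / -2.5 |
| 65% / 44% | 0–140 | 143 vs 141 | -0.2 / -0.6 / -0.9 |

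Example of a mean window (first 0–84 row): 0.65 × 170 + 0.35 × 65 = 133 and 0.65 × 184 + 0.35 × 79 = 147.

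**6. An extreme mix.** Let 35% of SEL-212 patients stop, all after dose 1 (30-day window), and 30% of Krystexxa patients stop with windows of 44 to 114 days in 14-day steps. At 30% risk by Day 170 the crude figures are 21.6% versus 27.0%, a gap of +5.3 points. At 50% risk the gap is +8.6.

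**7. Against chance.** With 75 per arm, the standard error of a difference is √(2p(1 - p)/75): 6.5 points at p = 20%, 8.2 at p = 50%.

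**The case against.** **Follow-up is handled in places.** SAP 7.2.5 models gout flares, which are AESIs, by Poisson regression with length of follow-up. SAP 6.1 plans Kaplan-Meier curves and log-rank tests for leaving the study because of an adverse event, and for stopping treatment because of the stopping rules or infusion-related reactions. SAP 8.1 tabulates and tests stopping-rule withdrawals by arm and period. It would be wrong to infer that time and differential stopping are ignored, or that a reader has nothing to judge them by. What stands is narrower: none of these adjusts the general TEAE, serious, related or AESI tables.

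**Withdrawn patients are still seen.** They attend to the end of Period 6, the schedules mark adverse events as collected continuously, and SAP 8.3 also says all adverse events will be summarised. So a reader should not infer that stopped patients go unobserved. But the parenthesis in the TEAE definition and the reporting period in Protocol 12.2.3.1 both close 30 days after the last dose, so later events are not TEAEs. If the window ran to the end of Period 6 for these patients, the stopping component would largely disappear. The texts disagree and need reconciling.

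**The Krystexxa minimum can be shorter.** The Per Protocol Set definition (SAP 5.5) mentions discontinuation at investigator discretion after at least one high pre-dose value. That could leave Day 0 as the last dose and a 30-day window. The 44 days is therefore the minimum under the stopping rule only.

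**The size is modest.** This is correct. The comparison is descriptive, the gaps lie at or below roughly one standard error, and events clustered early or around infusions are less affected by a late 14-day difference.

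**Conclusion.** The point holds in a limited form. The crude TEAE percentages mix event frequency with observation time, and observation time differs by arm by design. The day counts follow directly from the documents; the gap sizes rest on an assumed constant hazard and assumed stopping patterns. The schedule alone contributes at most 2.9 points. Across the main scenarios the gap runs from -4.6 to +6.0 points (Krystexxa minus SEL-212), and reaches +8.6 only if every stopped SEL-212 patient stops after the first dose.

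A reader might infer that the tables favour SEL-212. The documents do not support a direction. The shorter SEL-212 schedule lowers that arm's percentage, but if the planning rates of 65% and 44% approximate the shares not stopped, the sign reverses. Nor does this invalidate the safety comparison: the likely distortion is mostly smaller than sampling error. It is systematic, though, and inexpensive to make visible.

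**What to change.** - **SAP 8.1:** report TEAE time at risk by arm (total patient-years and distribution), beside the doses and stopping-rule table.
- **SAP 8.3:** keep the crude counts. For any, serious, related and AESI events, add exposure-adjusted incidence: patients with a first event per 100 patient-years at risk, with the arm difference and a 95% confidence interval. State that crude and adjusted figures are interpreted together.
- **Do not make the adjusted rate the sole basis of the safety statement.** It assumes a roughly constant hazard. With a common hazard three times higher in the first 30 days (30% risk by Day 170) and the extreme mix above, identical drugs give 88.6 (SEL-212) versus 82.3 (Krystexxa) per 100 patient-years. Patient-years is also a poor denominator for infusion reactions, with up to 6 versus 12 infusions.
- **Do not substitute a common cut at Study Day 170.** Early-stopped windows still close 30 days after the last dose. At 30% risk the +5.3 gap only shrinks to +3.9. In a mix with 65% versus 44% completing (SEL-212: 20% with 30 days, 15% with 58–142 days; other Krystexxa patients 44–114 days), the gap widens from -0.9 to -1.8. The cut would also leave 170 - 154 = 16 days after the last Krystexxa dose against 30 after the last SEL-212 dose.
- **Reconcile** the TEAE definition and reporting period (Protocol 12.2.1.1 and 12.2.3.1, SAP 8.3) with continued visits after withdrawal (Protocol 7.4.1) and continuous collection (Protocol Appendices A and C), so that time at risk has one definition.

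The cost is SAP wording and a few extra table columns; dosing dates and event onset dates are already recorded. The downside is the constant-rate assumption, which is why the crude counts stay.

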8.4. Laboratory Evaluations

Laboratory data will be summarized by the type of laboratory test and will be presented for each scheduled visit by treatment group (SEL-212 or KRYSTEXXA®). Normal reference ranges and markedly abnormal

This document is confidential.

results will be used in the summary of laboratory data. Data will be flagged according to the reference limits (High or Low), if applicable. Changes from baseline will be presented for each post-baseline visit. Shift tables of the number of patients with low/normal/high values at each scheduled post-baseline visit compared to the low/normal/high categorization at baseline will be provided by treatment group (SEL-212 or KRYSTEXXA®).

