7.1.2 Treatment Period

The total duration of treatment will be 6 months. Eligible patients will be randomized 1:1 prior to Baseline to receive SEL-212 or KRYSTEXXA.

Study patients in the SEL-212 arm will receive study drug every 28 days coinciding with Day 0 of each Treatment Period for a total of up to 6 infusions of SEL-212.

Study patients in the KRYSTEXXA arm will receive study drug according to the manufacturer's prescribing information, i.e., every 14 days coinciding with Day 0 and Day 14 of each Treatment Period for a total of up to 12 infusions of KRYSTEXXA.

Prior to infusion, all patients will receive a standardized regimen of premedication to minimize the potential for infusion reactions during study drug administration. After completing the study drug infusions, patients will remain at the investigational site for at least 1 hour for safety assessments.

Refer to [Section 10](#) for details about study drug administration.

With each dose, a blood sample will be drawn for assessment of SUA level immediately prior to infusion (ie, Time 0h) with SEL-212 or KRYSTEXXA, 1 hour after the infusion of the second component of SEL-212 or of KRYSTEXXA is completed. SUA levels will be assessed through additional post-infusion blood samples at pre-determined time points. Every effort will be made to obtain blood samples at the same time of day of each study visit.

[figure not shown]
Gout flares will be assessed at every visit. QoL and joint swelling and tenderness will be assessed on Day 0 of Treatment Period 1 and 4, and at the end of Treatment Period 6. Assessments of qualitative endpoints (health questionnaires and joint assessment) will be conducted on an assessor-blinded basis.

On dosing days, safety laboratory samples will be collected pre-infusion and per Schedule of Events in both the SEL-212 arm and the KRYSTEXXA arm. Concomitant medications and procedures and adverse events (AEs) will be monitored continuously during the study.

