10.6 Administration

10.6.1 SEL-212

Before administration of SEL-212, patients will be premedicated with antihistamines and steroids as described in [Section 10.5](#).

Patients will receive treatment with SEL-212 on Day 0 of each Treatment Period for a total of 6 doses of study drug.

All study drugs should be administered through the same IV access. All blood samples should be drawn from an alternative venous access.

If an infusion reaction occurs, Investigators are permitted to use concomitant medications or treatments deemed necessary to provide adequate patient care. Investigators should also utilize the infusion reaction lab kit provided in the Study Operations Manual to collect additional blood specimens. In the case of a Grade 3 or 4 infusion reactions occurring during an infusion, the administration of study drug should be immediately discontinued, and the affected patient should be treated according to the clinical trial site's protocol for infusion reactions (e.g., monitoring, administration of antihistamines, corticosteroids, fluids and epinephrine, as clinically indicated).

The reconstituted SEL-110.36 will be withdrawn from the vial and dosed via IV infusion with a syringe infusion pump utilizing an appropriately sized syringe. SEL-110.36 will be infused at a rate of 3.0 mL/hr for the first 30 minutes, then a rate adequate to deliver the remaining dose volume over a period of 60 minutes concurrently with 125 mL normal saline. Following the infusion of SEL-110.36, the main IV line must be flushed with normal saline prior to the start of the SEL-037 infusion. Refer to the Study Operations Manual for instructions regarding infusions for patients with medical history involving cardiovascular comorbidities.

SEL-037 infusion will start within 15 minutes after completion of the SEL-110.36 infusion. SEL-037 will be infused via infusion pump over a time period of no less than 120 minutes. If an infusion reaction occurs during the administration of SEL-037, the infusion may be slowed, or stopped and restarted at a slower rate at the discretion of the physician. Following the infusion of SEL-037, the main IV line must be flushed with normal saline.

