10.6.2 KRYSTEXXA

Before administration of KRYSTEXXA, patients will be premedicated with antihistamines and steroids as described in [Section 10.5](#).

Patients will receive treatment with KRYSTEXXA on Day 0 and Day 14 of each Treatment Period for a total of 12 doses of study drug.

All study drugs should be administered through the same IV access. All blood samples should be drawn from an alternative venous access.

KRYSTEXXA will administered based on the manufacturer's currently approved labeling (*KRYSTEXXA Prescribing Information 2018*). Detailed instructions for study drug administration are provided in the Study Operations Manual.

Before administration, the diluted solution of KRYSTEXXA should be allowed to reach room temperature, but never exposed to artificial heating (eg, hot water, microwave). The diluted solution of KRYSTEXXA should be administered by IV infusion via gravity feed, syringe-type pump, or infusion pump over no less than 120 minutes. Following the infusion of KRYSTEXXA, the main IV line must be flushed with normal saline.

If an infusion reaction occurs, Investigators are permitted to use concomitant medications or treatments deemed necessary to provide adequate patient care. Investigators should also utilize the infusion reaction lab kit provided in the Study Operations Manual to collect additional blood specimens. In the case of a Grade 3 or 4 infusion reactions occurring during an infusion, the administration of study drug should be immediately discontinued, and the affected patient should be treated according to the clinical trial site's protocol for infusion reactions (e.g., monitoring, administration of antihistamines, corticosteroids, fluids and epinephrine, as clinically indicated).

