12.2.1.5 Infusion Reactions / Adverse Events of Special Interest

A study drug-related AE that occurs within 24 hours after initiation of study drug infusion will be assessed as an infusion reaction. An infusion reaction suspected to be anaphylaxis will be assessed according to the clinical criteria for the diagnosis of anaphylaxis based on the National Institute of Allergy and Infectious Diseases (NIAID) / Food Allergy & Anaphylaxis Network (FAAN) Symposium criteria ([Sampson 2006](#)).

Infusion reactions will be managed and treated as described below. In addition to premedication with antihistamines and steroids ([Section 10.5.2](#)), the following steps will be implemented in this protocol to either reduce the risk of infusion reactions or manage infusion reactions.

- Patients with immunoreactivity to PEG will be ineligible for the study
- Patients with prior exposure to uricase therapy will be ineligible
- Patients with a history of anaphylaxis or severe allergic reactions, angioedema, or previous infusion reactions will be excluded from the trial.
- Study drug will be administered at controlled rates only in a healthcare setting and by healthcare providers sufficiently equipped and prepared to manage infusion reactions including anaphylaxis.
- In case of infusion reaction, sites will perform specific assessments as specified in the Study Operations Manual.
- Each patient will be observed for infusion reactions after dosing of study drug in the clinic for approximately 1 hour after the end of study drug infusion. Patients will be informed about the signs or symptoms of infusion reactions and will be instructed to notify the Investigator immediately if they believe they are experiencing a reaction.
- Each patient shall remain for a minimum of 1 hour after the completion of infusion of study drug for a period of safety observation.
- Only sites with immediate capability to appropriately respond to a reaction of this severity will be allowed to participate in the trial to reduce the risk to any patient.

Adverse events of special interest (AESI) will be recorded specifically for occurrences of: gout flares, infections, viral infections, interstitial lung disease, stomatitis, infusion-related reactions including anaphylaxis, malignancies, renal failure; and the following lab tests, if deemed

clinically significant by the PI: hyperlipidemia, worsening of renal function tests, proteinuria, and leukopenia.

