08 JUN 2020

20. APPENDICES

APPENDIX A SCHEDULE OF ASSESSMENTS FOR PATIENTS RANDOMIZED TO SEL-212

Assessment	Scr.		Treatment Period (TP)																EOS ¹	ET		
			TP1 ²		TP2 ²		TP3 ²				TP4 ²		TP5 ²		TP6 ²							
Day	-45 d	-7 d ³	D0	D21	D0 ⁴	D21	D0 ⁴	D7	D14	D21	D0 ⁴	D21	D0 ⁴	D21	D0 ⁴	D7	D14	D21	D28 ²⁰			
Informed Consent	X																					
Demographics	X																					
Inclusion/Exclusion	X																					
Medical History	X																					
Physical Examinations	X ⁵		X ⁶		X ⁶		X ⁶				X ⁶		X ⁶		X ⁶					X ⁵		X ⁵
Vital Signs	X	X	X ⁷		X ⁷		X ⁷				X ⁷		X ⁷		X ⁷		X	X	X			X
Weight and Height ⁸	X	X		X		X				X		X		X				X	X			X
Tophus Assessment	X																			X		X
12-Lead ECG	X																			X		X
Screening Labs ⁹	X																					
Screening Lab: Anti-PEG-Ab	X																					
Urine Pregnancy Test	X																					
Washout: ULTs		X ¹⁰	Patients will abstain from ULT use after the ULT washout period																			
Document ULTs Discontinued		X																				
Dispense Premedication: Gout Flare and Infusion Reaction		X																				
Premedication: Gout Flare		X ¹¹	Continuously																			
Premedication: Infusion Reaction			X ¹²		X ¹²		X ¹²				X ¹²		X ¹²		X ¹²							
Safety Labs: Chemistry ¹³	X		X	X		X				X		X		X					X	X		X
Safety Labs: Hematology ¹⁴	X		X	X		X				X		X		X				X	X		X	
Safety Labs: Coagulation ¹⁵	X		X	X		X				X		X		X				X	X		X	
Safety Labs: Lipids ¹⁶	X		X	X		X				X		X		X				X	X		X	
Safety Labs: Urinalysis ¹⁷	X		X	X		X				X		X		X				X	X		X	
Safety Labs: Anti-drug-Ab																			X		X	
Gout Flare Assessment	X		X	X	X	X	X	X	X	X	X	X	X	X	X	X	X	X	X	X	X	
Joint Assessment (tenderness, swelling)			X								X								X		X	

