5.8. Key Definitions

Baseline is defined as the last non-missing value prior to the start of infusion of SEL-212 or KRYSTEXXA®.

Day 0 of Treatment Period 1 is defined as the first date of study drug administration.

Study day within each treatment period will be calculated as date of event/collection – first dose date at each treatment period to be consistent with protocol defined day 0.

Overall study day will be calculated as date of event/collection – first dose date of the study.

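### Six of the seven scheduled post-baseline safety-lab visits are not like-for-like between arms for steroid-sensitive tests: SEL-212 is sampled on non-dosing Day 21, Krystexxa on premedicated dosing Day 14

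*SAP*

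**What the plan says.** SAP 8.4 (Laboratory Evaluations) presents each laboratory test by scheduled visit and treatment group, with high/low flags, changes from baseline and shift tables: "Changes from baseline will be presented for each post-baseline visit". SAP 5.8 fixes the reference point: "Baseline is defined as the last non-missing value prior to the start of infusion of SEL-212 or KRYSTEXXA". Safety labs are scheduled on Day 0 of Treatment Period 1 (TP1), so that sample normally replaces the Screening sample as baseline.

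In Protocol Appendix A the row "Safety Labs: Hematology" and its companion safety-lab rows are marked at Screening, TP1 Day 0, Day 21 of every period and TP6 Day 28. Protocol 10.6.1 states the dosing days: "Patients will receive treatment with SEL-212 on Day 0 of each Treatment Period". In Appendix C the same rows are marked at Screening, TP1 Day 0, Day 14 of every period and TP6 Day 28. Day 14 is a Krystexxa dosing day, and Protocol 10.6.2 says "Before administration of KRYSTEXXA, patients will be premedicated with antihistamines and steroids".

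Protocol 10.5.2 gives the steroid timing for both arms: oral prednisone 40 mg about 24 (±12) hours before dosing and IV methylprednisolone 40 mg about 1 (±0.5) hour before. Protocol 7.1.2 says of the lab draw: "On dosing days, safety laboratory samples will be collected pre-infusion and per Schedule of Events in both the SEL-212 arm and the KRYSTEXXA arm". SAP 8.4 mentions neither premedication nor how Day 14 relates to Day 21.

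**The concern.** Drawing blood before the infusion does not mean drawing it before the steroid, because the premedication also precedes the infusion. A Krystexxa Day 14 sample from a patient still on drug can carry an acute steroid effect. A SEL-212 Day 21 sample comes about three weeks after the last premedication and should not.

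For tests that respond to steroids, the by-arm columns can then differ even if the two drugs have identical laboratory effects. If steroid raises white cells and glucose (an assumption; the documents give no figures), SEL-212 could appear to lower white cells relative to Krystexxa, and a real glucose rise on SEL-212 could be obscured. Protocol 6.2.3 makes laboratory review part of a safety comparison with Krystexxa. The laboratory events of special interest in Protocol 12.2.1.5 include "hyperlipidemia, worsening of renal function tests, proteinuria, and leukopenia", so a reader will look at the white-cell tables.

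**Working it through.** The plan states no figure to reproduce on this point. The check is a count from the schedules, followed by simple algebra.

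**Count.** Early termination and the telephone end-of-study contact are excluded.

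| | SEL-212 (Appendix A) | Krystexxa (Appendix C) |
|---|---|---|
| Post-baseline lab visits | Day 21 of TP1 to TP6; TP6 Day 28 | Day 14 of TP1 to TP6; TP6 Day 28 |
| Number | 7 | 7 |
| On a dosing day | 0 | 6 |

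Six of seven visits differ between arms in study day and, for patients still on Krystexxa, in steroid status. TP6 Day 28 (Study Day 168) follows the last scheduled infusion by 168 − 140 = 28 days for SEL-212 and 168 − 154 = 14 days for Krystexxa. Neither arm has recent premedication there.

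**Direction.** Define:
- b: mean steroid shift in the TP1 Day 0 sample, expected to be equal in the two randomized arms;
- d: mean steroid shift in a Day 14 sample from a Krystexxa patient premedicated for that dose;
- f: fraction of Krystexxa patients sampled at that visit who are still on drug;
- eS and eK: the true drug effects.

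Assume the acute shift has gone by 14 days. Then:
- SEL-212 change at Day 21 = eS − b
- Krystexxa change at Day 14 = eK + f·d − b
- Difference = (eS − eK) − f·d

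Three things follow.
1. The between-arm offset is −f·d whatever the value of b.
2. Taking Screening as baseline sets b to zero but leaves −f·d in place. It alters only the within-arm changes and shifts.
3. At TP6 Day 28 both changes carry −b, so the between-arm difference is free of this offset, while each arm's own change is not.

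**Size.** The documents give no value for d or f. In units of the SD of the change, with 75 per arm, the standard error of a difference is √(2/75) = 0.163 SD.

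| Assumed f·d (SD) | 0 | 0.1 | 0.25 | 0.5 | 1.0 |
|---|---|---|---|---|---|
| In standard errors | 0 | 0.6 | 1.5 | 3.1 | 6.1 |

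Dilution matters. Protocol 7.4.1.2 keeps withdrawn Krystexxa patients in the visit schedule without infusions. Purely for illustration, set f to the 44% Krystexxa response rate assumed in Protocol 13.1 (not a stated on-drug fraction). Then d = 0.5 SD gives 0.44 × 0.5 = 0.22 SD, or 0.22 / 0.163 = 1.3 standard errors, ignoring the extra variance from mixing the two groups. The offset therefore changes over time with treatment failure in that arm.

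**The case against.** The strongest reply is that the plan makes no formal laboratory comparison. SAP 8.4 is descriptive, has no test, and has no rule pairing Day 14 with Day 21. As different scheduled visits they may well appear as separate rows. This stands: a reader might infer that a planned test is biased or an error rate inflated, and the documents do not support that. What remains is that by-arm columns invite comparison, and nothing in the SAP warns against it.

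A reader might also infer that every baseline follows prednisone. That does not hold. The revision history dates the 24-hour oral steroid to version 2.1 (03 FEB 2020). On the synopsis's estimated dates the last patient completes on 31 July 2020; subtracting 168 days of treatment puts the last first dose near 14 February 2020. On those planned dates most baselines would predate that version, as would many Day 14 samples. The IV steroid remains, but the documents do not say whether blood is drawn before or after it. Both b and d could be near zero for some patients and can vary with enrolment date.

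It is tempting to read the schedule as producing false leukopenia events on SEL-212. The documents do not establish this. A laboratory event of special interest requires the investigator to judge it clinically significant. High/low flags use raw values, and the SEL-212 Day 21 values are the ones without recent steroid.

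Nor is Protocol 7.1.2 flatly contradicted by Appendix A. Its reference to the schedule allows the reading that labs which fall on a dosing day are drawn before infusion, as at TP1 Day 0. The wording is unclear, because SEL-212 has no later dosing-day safety labs.

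Finally, Screening is no clean replacement baseline. It can be up to 45 days old, is truncated by the eligibility limits (for example on white cells and glucose), and out-of-range tests may be repeated up to twice. That invites regression to the mean in the very tests concerned.

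**Conclusion.** The point holds as a limit on interpretation. At six of seven scheduled post-baseline lab visits, the by-arm summaries, changes and shifts in SAP 8.4 are not like-for-like for steroid-sensitive tests. The exposed results are mainly white cells with differential and glucose.

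The schedule mismatch is certain from the appendices; the size of its effect is not. It depends on the acute steroid shift, the order of draw and IV steroid, the protocol version in force, and how many Krystexxa patients are still on drug. Zero is within the plausible range for some patients. The conclusion also assumes that the acute effect has gone by 14 days. Only TP6 Day 28 gives a between-arm comparison free of this mechanism. This is a worthwhile, inexpensive improvement to descriptive safety tables; it does not affect the efficacy analysis.

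**What to change.** In SAP 8.4:
- Name TP6 Day 28 as the between-arm laboratory comparison for values, changes and shifts.
- Present SEL-212 Day 21 and Krystexxa Day 14 as within-arm summaries.
- Show steroid premedication status (yes/no before the draw) at baseline and at each lab visit. The documents do not say whether clock times of premedication are recorded. If they are not, show whether each scheduled steroid was taken and footnote that its order relative to the draw is unknown.
- Keep the SAP 5.8 baseline. Add change from Screening as a supplementary display for white cells with differential and for glucose, with a note on the age of Screening values and their truncation by eligibility limits.

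In Protocol 7.1.2 and the synopsis, clarify the dosing-day lab sentence so that it agrees with Appendix A.

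The cost is SAP wording and a few table shells, with no new samples. The drawback is that TP6 Day 28 is a single late visit, and the arms still differ there in time since last scheduled dose (28 versus 14 days). No change to dosing or premedication is proposed.
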